8 STUDY ENDPOINTS

The primary study endpoint is measuring early recovery of postoperative course by calculating early return of bowel motion (passing flatus and/or stool on which postoperative day), presence or absence of nausea and/or vomiting, presence or absence of chest symptoms (cough, sputum

PROTOCOL TITLE: Does increased mobility assessed with 3D motion tracking technology lead to early post-operative recovery among patients undergoing oncologic surgeries

and ability of using incentive spirometry), early discharge from the hospital and 30 days surgical related complications and readmissions.

The secondary study endpoint is measuring the range of joint movement in upper and lower joints of body, using the 3D motion tracking system (Xsens), to identify the minimum required level of mobility for better early postoperative course recovery.

A few other secondary endpoints concluded from the post experiment questionnaire include: assessing encouraged walking in the hospital setting subjectively improves their exercise habit outside of the hospital, how was the application of the sensors in a hospital setting as this is the first study to do so, and to assess the subjective impact of complications on quality of life.

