16 STATISTICAL PLAN

Demographics: Subject demographic and clinical characteristics will be reported by group using the appropriate descriptive statistics and graphical summaries. Comparisons will be made between groups using the Mann-Whitney U or Chi-square tests, as appropriate.

Randomization: Subjects will be randomized to the control and intervention groups in a 1:1 fashion using a permutation block design (block sizes = 4). The randomization list will be developed by the study statistician.

Primary Analysis: The primary objective is to evaluate changes in mobility between the control (standard of care) and intervention (additional activity) groups. The primary outcomes are measures of mobility (i.e. range of movement), which are treated as continuous measures and will be summarized by group and time-point using the mean, median, and standard deviation. The measures of mobility will each be modeled as a function of treatment group, time post-surgery, their two-way interaction, and random subject effects using a linear mixed model. Within each group, the effect of time on the mean will be evaluated using tests about the appropriate contrasts of model estimates. The effect of the two groups on the time-mobility relationship will be evaluated using an F-test about the interaction term. All model assumptions will be evaluated graphically and transformations will be applied as necessary.

Secondary Analyses: The secondary objective is to evaluate the impact on post-surgical complications. The complication status (present/absent) and grades will be summarized by group and compared using Fisher's exact test or the chi-square test, as appropriate.

PROTOCOL TITLE: Does increased mobility assessed with 3D motion tracking technology lead to early post-operative recovery among patients undergoing oncologic surgeries

The association between complication status and changes in measures of mobility may be evaluated using logistic regression models.

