Sample Size Determination: The power calculations are based on the primary analysis, which compares the changes in measures of mobility between the two groups. Since the form of the models is unknown beforehand, a simplified and conservative power calculation is based on comparing the mean change (baseline to discharge) in a given mobility measure between groups using a two-sided, two-sample t-test. With a sample size of n=40 per group, we have 80% power (at $\alpha = 0.05$) to detect a difference of at least 0.63 standard deviations. Such a moderate effect size would be considered clinically relevant.

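### If Section 16 governs, several range-of-movement measures are primary, with no deciding measure, success rule or multiplicity adjustment; the 80% power covers one measure under a t-test, not the planned F-tests

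*Combined protocol and SAP*

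**What the plan says.** All references are to the combined protocol and SAP.

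- **Section 16, Primary Analysis.** The outcomes are plural: "The primary outcomes are measures of mobility (i.e. range of movement), which are treated as continuous measures". Each gets its own linear mixed model: "The measures of mobility will each be modeled as a function of treatment group, time post-surgery, their two-way interaction, and random subject effects". The arms are compared as follows: "The effect of the two groups on the time-mobility relationship will be evaluated using an F-test about the interaction term".
- **Section 16, Sample Size Determination.** The scope is the plural analysis: "The power calculations are based on the primary analysis, which compares the changes in measures of mobility between the two groups". The calculation itself is for one unnamed measure: "comparing the mean change (baseline to discharge) in a given mobility measure between groups using a two-sided, two-sample t-test". It gives 40 per group, 80% power, alpha 0.05 and a difference of 0.63 SD.
- **Section 8.** The ranking is the reverse: "The primary study endpoint is measuring early recovery of postoperative course", while "The secondary study endpoint is measuring the range of joint movement in upper and lower joints of body".

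No section lists the measures, says which one decides, says how many must be significant, or describes an adjustment across them.

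**The concern.** Each mobility measure has its own model, so the natural reading is one between-group F-test per measure, although the F-test sentence does not itself repeat the word each. Section 8 refers to both upper and lower joints, so there are at least two candidates. Without a named measure or success rule, the joint, the movement and the criterion for success could all be settled after the data are seen. A significant result in one joint could then be reported as the primary finding at 0.05 when it was one of several chances.

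The power statement has a related gap. It is introduced as covering the primary analysis, yet it describes one measure and a test other than the one the plan will run.

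**Working it through.** **Inputs from Section 16:** 40 per arm, 1:1 allocation, two-sided alpha 0.05, difference 0.63 SD of change.

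**Assumptions, not in the documents:** number of measures m = 2, 4 or 6; equal correlation r between measures of 0, 0.5 or 0.9; the success rule; the number of time points.

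**1. The plan's own figure.** Two-sample t-test with df = 2 × 40 − 2 = 78 and noncentrality 0.63 × √(40/2) = 2.817. The critical value is 1.991. Exact power is 79.5%; the normal approximation gives 80.4%. Exact 80% power is reached at 0.634 SD. The stated figure reproduces for one measure under this test.

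**2. Any one significant measure counts.** With r = 0, family-wise error is 1 − 0.95^m: 1 − 0.9025 = 9.8% for m = 2, and 1 − 0.8145 = 18.5% for m = 4. For r > 0, it comes from numerical integration over equicorrelated normal statistics.

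| m | r = 0 | r = 0.5 | r = 0.9 |
|---|---|---|---|
| 2 | 9.8% | 9.1% | 7.0% |
| 4 | 18.5% | 15.6% | 9.4% |
| 6 | 26.5% | 20.7% | 10.8% |

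Simulating the interaction F-test itself under no effect (2, 3 and 5 time points, complete balanced data, random intercept) gives nearly the same ranges: 7-10%, 9-19% and 11-27%. Under this rule the chance of at least one significant result rises: with a true 0.63 SD effect on every measure it is 85-96% for m = 2.

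**3. All measures must be significant.** Type I error is not inflated. With a true 0.63 SD effect on every measure and r = 0, joint power is 0.795^m: 63% for m = 2, 40% for m = 4 and 25% for m = 6. With r = 0.9, simulated t-tests give 74%, 69% and 67%.

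**4. Equal split of alpha (0.05/m) at 40 per arm.** Power per measure is 70%, 60% and 55% for m = 2, 4 and 6. Restoring 80% would need 50, 58 or 63 per arm.

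**5. The planned F-test for one measure.** Assume a random intercept, complete data and time as a category with T levels. A change SD of 1 means residual variance 0.5. With d_t the arm difference at time t, the noncentrality is λ = (40/2) × Σ(d_t − mean d)² / 0.5, on T − 1 and 78(T − 1) df. The baseline-to-discharge difference is fixed at 0.63.

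| T | Pattern | λ | Power |
|---|---|---|---|
| 2 | only one possible | 7.94 | 79.5% |
| 3 | linear divergence | 7.94 | 70.5% |
| 5 | linear divergence | 9.92 | 70.5% |
| 3 | one step, first or last interval | 10.58 | 83.0% |
| 5 | one step, first or last interval | 12.70 | 82.1% |

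The t-test and the F-test agree only when there are two time points.

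**The case against.** **Section 8 makes recovery primary.** The title and objectives also point that way. If Section 8 governs, what remains is unadjusted testing in a secondary family, which is often acceptable when no confirmatory claim is made. This stands, and is why the point is conditional. Against it, Section 16 is the only place that sets out a primary analysis, and the power calculation is tied to that analysis.

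**The sizes rest on assumptions.** True: the count, the correlation and the success rule are all absent. A reader might infer that this trial's error rate is 19% or 26%; the documents do not support any such figure. The ranges show direction, and the mildest case shown (two measures, r = 0.9) still gives 7.0% error under the any-one rule or 74% joint power under the all rule. Appendix A appears in the available text only as a heading, so a list of measures could have stood there; it is unlikely to have held a success rule.

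**The plan never claims family-wise power.** Correct. The calculation openly concerns one measure. The gap is that it is offered as the basis for a plural primary analysis.

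**Two stronger readings are tempting.** One is that each measure tested alone has 80% power and a secure 5% error rate, so that naming one measure settles everything. The documents do not support this. The 79.5% belongs to the t-test on change, and the F-test can fall on either side of it. The nominal 5% is also not assured. Section 9 excludes and replaces patients who cannot complete walking tasks that differ by arm, and Section 16 allows transformations as needed. Tracking until discharge means that the number of time points may vary by patient. The other reading is that type I error is inflated whatever the rule; under an all-must-succeed rule it is not.

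**Conclusion.** The point holds, conditionally on Section 16 governing. The primary family then has no defined family-wise error or joint power. Which property fails depends on the missing success rule: error rises to about 7-10% for 2 measures and 9-19% for 4 if any one counts, and joint power falls below 80% if all must succeed. These are illustrations over assumed counts and correlations from 0.9 to 0.

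The stated power is correct for its own simplified test on one measure. For the planned F-test it is about 70% to 83% in the 3- and 5-time-point cases worked above, under a random intercept and complete data. If Section 8 governs, the same gap sits in a secondary family and matters less. It should be corrected; confidence is medium because of that unresolved conflict.

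**What to change.** 1. Reconcile Section 8 with Section 16 on whether early recovery or mobility is primary.
2. If mobility is primary, pre-specify one range-of-movement measure, or one summary across the joints already recorded, with one group comparison carrying two-sided 0.05. Name it in Sample Size Determination in place of the generic reference to a given measure.
3. Either make the baseline-to-discharge change contrast the deciding comparison, so that the existing calculation matches it, or state that the 80% refers to the t-test on change and not to the interaction F-test.
4. Report the other measures as secondary, for example with a Holm adjustment, or with confidence intervals and no confirmatory claim.
5. If Section 8 governs, label the mobility tests as a secondary family and restate the calculation as power for a secondary endpoint.

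**Cost.** If mobility is primary: a few sentences in Sections 8 and 16, with no new data. Forty per arm still gives 79.5% power for the t-test on change in the named measure at 0.63 SD. The downside is that an effect confined to other joints cannot be claimed as primary and could be missed by the primary test. If Section 8 governs, relabelling is still a text change, but powering a recovery endpoint is a separate and larger task that this fix does not address.

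### Ordered complication grades are compared with tests that ignore their order; an ordinal main comparison would use the data better if severity shifts consistently

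*Combined protocol and SAP*

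**What the plan says.** Section 16 sets the aim for this outcome: "The secondary objective is to evaluate the impact on post-surgical complications". It handles presence and grade in one sentence with one pair of tests: "The complication status (present/absent) and grades will be summarized by group and compared using" Fisher's exact or chi-square, whichever suits.

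Two other sentences in section 16 could have supplied an analysis that uses the order, but neither does:
- "The association between complication status and changes in measures of mobility may be evaluated using logistic regression models". This model is optional, uses status rather than grade, and relates complications to mobility rather than comparing the arms.
- "Comparisons will be made between groups using the Mann-Whitney U or Chi-square tests, as appropriate". This belongs to the paragraph on demographic and clinical characteristics, so the rank test named there does not extend to grades.

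The documents do not name a grading scale, say how many grades there are, or say which grade counts for a patient with several complications. They give no expected rate or effect. The only power statement concerns mobility.

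**The concern.** Fisher's exact and chi-square tests on a table of grades give the same p-value if the grade labels are shuffled. If the intervention moves patients consistently towards milder grades, an ordinal test puts that signal into one degree of freedom. The unordered test spreads it over one fewer degrees of freedom than there are categories. A significant unordered result says only that the two distributions differ. It does not say which arm did better or by how much.

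This matters because complications are the only clinical outcome for which section 16 specifies a comparison between arms; its other comparison of outcomes is of mobility. With 40 patients per arm there is little information to spare.

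**Working it through.** **1. The plan's own figure.** Section 16 says "With a sample size of n=40 per group" and bases its calculation on a "two-sided, two-sample t-test", with 80% power at 0.05 for 0.63 SD. The exact noncentral-t calculation gives 79.5% power at 0.63 SD and a detectable difference of 0.634 SD at 80%. The figure reproduces, but it concerns mobility. There is no stated figure for grades to check.

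**2. General cost of ignoring order.** Take a 1-df trend test with 80% power, so the noncentrality is λ = (1.960 + 0.842)² = 7.85. If an unordered test on d degrees of freedom has the same λ, its power is P(χ²_d(λ) > χ²_d,0.95). This gives 71%, 65%, 60% and 56% for d = 2, 3, 4 and 5. Restoring 80% takes about 23% to 63% more patients.

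**3. Illustration at 40 per arm (assumed inputs).** Control: none 50%, then 20%, 15%, 10% and 5% in rising severity. The intervention arm follows a common odds ratio (OR): each cumulative odds of being at or below a grade is multiplied by the OR. At OR 2 the cumulative odds 1, 2.33, 5.67 and 19 become 2, 4.67, 11.33 and 38. The intervention distribution is then 66.7/15.7/9.5/5.5/2.6%. Simulated power at two-sided 0.05:

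| Test | OR 2.0 | OR 2.5 | OR 3.0 |
|---|---|---|---|
| Chi-square on grades | 19% | 30% | 42% |
| Rank test on grades | 36% | 53% | 68% |
| Chi-square, present/absent | 35% | 52% | 65% |
| Fisher's exact, present/absent | 27% | 41% | 56% |

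Repeat simulations agree to within one or two points. The rank test's type I error is about 5%.

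**4. Other assumed distributions.** Power of chi-square on grades / Fisher's exact on grades / rank test:

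| Control grades | OR 2 | OR 3 | OR 4 |
|---|---|---|---|
| 75/10/10/5% | 12 / 15 / 23% | 23 / 31 / 43% | 34 / 36 / 57% |
| 50/20/17/10/3% | 18 / 17 / 35% | 42 / 43 / 67% | 62 / 63 / 83% |
| 40/25/20/15% | 25 / 26 / 38% | 53 / 56 / 72% | 75 / 76 / 89% |

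The loss against the rank test is 11-24 points for chi-square and about 7-24 points for Fisher's exact.

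**5. Severity falls more than incidence.** Control 30/20/20/20/10%, intervention 40/32/16/9/3%. Any complication falls from 70% to 60%, an OR of (0.70/0.30)/(0.60/0.40) = 1.56. The two worst categories together fall from 30% to 12%, an OR of (0.30/0.70)/(0.12/0.88) = 3.14. Power: present/absent chi-square about 16%, chi-square on grades 38%, rank test 46%.

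**6. Only the mix of grades changes.** The share with no complication is 50% in both arms.
- Control 50/20/15/10/5%, intervention 50/40/5/3/2%: chi-square on grades 51%, rank test 13%.
- Non-monotone change, control 50/30/10/7/3%, intervention 50/10/30/7/3%: 63% against 10%.

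**The case against.** The strongest reply is that the same sentence also tests present/absent status. With 50% affected in the control arm and 25% in the intervention arm (OR 3), the expected count is (20 + 10)/2 = 15 per arm, so chi-square is the natural choice. Its 35/52/65% is almost the rank test's 36/53/68%. This stands: under proportional odds the plan as a whole loses little chance of finding an effect on complications. But that test answers whether any complication occurred, not how bad it was, and step 5 shows it falling behind when severity moves more than incidence.

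The second reply is that the unordered test can win, and step 6 shows this. A reader might infer that changing the test has no downside; that is not so. The unordered test's gain, however, comes from responding to any difference at all, including one with no clear direction.

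A reader might also infer that the plan loses much of its power whatever happens, or that sparse grades hurt the unordered test most. The documents support neither. They give no distribution from which to derive a loss. At OR 3 in step 4, the Fisher loss is 12 points in the sparsest scenario against 24 and 16 in the denser ones.

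Finally, section 16 makes this a secondary comparison with no claimed power, and the rank test does not exceed 72% in steps 3 and 4 for odds ratios up to 3. That limits the consequence, but it does not justify discarding the order.

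**Conclusion.** The point holds in a conditional form. The plan applies unordered tests to an ordered outcome, and no other analysis in it makes up for this. For a consistent shift towards milder grades at 40 per arm, the grade comparison has about 19-42% power where a rank test would have 36-68%, at odds ratios of 2 to 3 and assumed control grades of 50/20/15/10/5%. These sizes rest entirely on assumed distributions, a proportional-odds shift and one grade per patient. The documents fix none of these.

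The present/absent chi-square offsets most of the loss in that setting, though not as a measure of severity. The advantage reverses when only the mix of grades changes. The mobility sample size is unaffected. This is a cheap improvement, not a flaw that invalidates the trial.

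**What to change.** In section 16, Secondary Analyses:
- Name the grading scale, and define the graded outcome as each patient's highest complication grade, with none = 0.
- Make the Wilcoxon rank-sum test, or proportional-odds regression reporting an odds ratio with 95% CI, the main comparison of grades between arms. Choose one in advance.
- Keep Fisher's exact or chi-square for present/absent status.
- Show the grade table by arm descriptively, or keep the unordered test on grades as supportive. This retains a view of changes in grade mix that the ordinal test can miss.

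The cost is a sentence or two in the plan, with no extra patients or visits. The price is lower power when only the grade mix changes or the change is non-monotone (for example 13% against 51%). The comparison should still be reported as an underpowered secondary analysis.

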9 PROCEDURES INVOLVED

This is a prospective randomized controlled trial comparing the early postoperative course of patients who undergo inpatient oncological procedures after assessment of their baseline physical activity before the surgery, using validated questionnaires in the clinic, to have a homogenized sample for the study. Participants will be randomized to the control arm (40 participants) and intervention group (40 participants). Control group participants will be asked to walk one to two laps around the ward twice per day, on the first day after the surgery following the usual clinical practice at Roswell Park Comprehensive Cancer Center-urology department (RPCCC). Their movement will be tracked with 3D motion tracking system (Xsens). The intervention arm participants will be asked to walk for minimum 30 minutes per day and their movement also will be tracked with Xsens. In both arms the patients will be asked to mobilize (walk out of the bed) on first day post-surgery under supervision and assistant of attending nurse in the floor if their clinical situation allowed. If patient cannot complete the walking tasks, they will be excluded from the study and they will be replaced by recruiting other patients.

Xsens is a wireless technology that makes use of sensors. The sensors are applied in a non-invasive manner and do not require the suit to be applied. There are various configurations of the sensors that can be utilized. The minimum number of sensors needed is 7. They are applied by using Velcro bands. The entire set-up takes about 5-10 minutes.

The study duration is 24 months or until target accrual is reached. In both arms their mobility will be tracked till they discharged from the hospital. In both arms we will assess the symptoms and signs of gastro-intestinal complications (nausea, vomiting, abdominal pain, passing flatus or stool) and chest symptoms (coughing, sputum, utilizing incentive spirometry) until they are discharged from the hospital. We will continue to follow them for 30 days post discharge to note any complications or readmission.

Patients at standard follow ups, 2 weeks, 6 weeks, 3 months or over the phone will complete a short post study questionnaire (Appendix B). The last three questions are taken from Woodfield et al., who assessed postoperative problems from the perspective of the patient on the identification of complications after surgery (11).

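### If complications turn out sparse, Boschloo's exact test in place of Fisher's would recover some power for complication status at 40 per arm: about 5 to 19 points for large effects, 1 to 4 for a halving

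*Combined protocol and SAP*

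**What the plan says.** Section 16 (Statistical Plan, Secondary Analyses) makes post-surgical complications the secondary objective. It states: "The complication status (present/absent) and grades will be summarized by group", and then "compared using Fisher's exact test or the chi-square test, as appropriate". It gives no rule for choosing between the two tests, and no significance level, expected complication rate or power for this comparison.

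The only power statement is for mobility. It has "With a sample size of n=40 per group", is made "using a two-sided, two-sample t-test", and claims 80% power at a 5% level "to detect a difference of at least 0.63 standard deviations". Allocation is 1:1. Section 9 says of patients who cannot complete the walking tasks that "they will be excluded from the study and they will be replaced by recruiting other patients", so 40 per arm is the number to use for complications as well.

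**The concern.** Fisher's test conditions on the total number of events. When that total is small, few outcomes are possible and the attainable error rate falls well below 5%. A conventional two-step rule sends exactly those tables to Fisher. An unconditional exact test uses the same data, also keeps the error rate within 5%, and can reject more often.

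At stake is whether a sparse but lopsided result, such as five complications in one arm and none in the other, is reported as non-significant only because of the test chosen. The trial was sized on mobility, so the complication comparison has little power to spare.

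**Working it through.** **The plan's own figure.** For 40 per arm and 0.63 SD: 0.63 × √(40/2) = 2.817; 2.817 − 1.960 = 0.857; Φ(0.857) = 80.4%. The noncentral t gives 79.5%, with a detectable difference of 0.634 SD at 80% power. The stated 80% reproduces, but it concerns mobility only.

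**Inputs.** From the documents: 40 per arm, 1:1. Assumed: the two-sided 5% level stated for mobility also applies to complications; Fisher is used when the smallest expected count is below 5; and all complication rates.

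**Where Fisher applies.** With T complications in total, the smaller expected count per arm is 40 × T/80 = T/2. It is below 5 when T is below 10.

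**Method.** All 41 × 41 possible tables were enumerated under two independent Binomial(40, p) distributions. Power is the sum of P(X = a) × P(Y = b) over the rejected tables. Boschloo's test uses Fisher's p-value as its statistic and maximises the tail probability over the common rate.

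**Which verdicts change.** Boschloo rejects every table that Fisher rejects. With T below 10 it adds two patterns and their mirror images:
- 5 v 0: Fisher p = 2 × C(40,5)/C(80,5) = 2 × 658,008/24,040,016 = 0.055; Boschloo p = 0.033.
- 7 v 1: Fisher p = 2 × [40 × C(40,7) + C(40,8)]/C(80,8) = 2 × 822,647,085/28,987,537,150 = 0.057; Boschloo p = 0.033.

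**Error rate at a common complication rate.**

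| Common rate | Fisher alone | Two-step rule (Fisher/chi-square) | Two-step rule (Boschloo/chi-square) |
|---|---|---|---|
| 5% | 0.4% | 0.4% | 1.5% |
| 10% | 1.7% | 2.6% | 3.9% |

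Boschloo used alone has a maximum of 4.8% over all rates. Both two-step rules peak at 5.7%, at a 50% rate, because of the chi-square branch.

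**Power, with only the Fisher branch replaced.**

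| True rates | With Fisher | With Boschloo | Gain (points) |
|---|---|---|---|
| 12.5% v 0% | 38.4% | 57.1% | 18.8 |
| 10% v 1% | 15.2% | 27.7% | 12.5 |
| 15% v 3% | 31.8% | 42.2% | 10.4 |
| 15% v 5% | 22.2% | 28.4% | 6.2 |
| 20% v 5% | 48.2% | 53.4% | 5.2 |
| 10% v 5% | 5.1% | 8.8% | 3.7 |
| 15% v 7.5% | 13.7% | 16.7% | 2.9 |
| 20% v 10% | 22.7% | 23.8% | 1.1 |
| 30% v 15% | 36.5% | 36.6% | about 0 |

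Gains are taken before rounding. As a check, the gain at 12.5% v 0% must equal the chance of 5 v 0, because 7 v 1 cannot occur: C(40,5) × 0.125⁵ × 0.875³⁵ = 18.8%.

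**How general is it?** On a one-point grid of 156 pairs of rates averaging below 12.5%, the median gain is 5.6 points. It is at least 5 points in 52% of pairs. That share is 74% when the true difference is at least 5 points, and 91% when it is at least 10.

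**The case against.** The case for leaving the plan alone is that Fisher's test is valid, that conditional versus unconditional exact testing is a choice between accepted methods, and that the trial was not powered on complications. That stands, so nothing here is a defect of validity.

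Four stronger readings are tempting, and none is supported.

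- **That the tables will be sparse.** The documents give no complication rate. The endpoint is any complication, follow-up runs to 30 days after discharge, and any inpatient oncologic surgery qualifies. At 20% v 10%, fewer than 10 events occur in about 22% of trials; at 30% v 15%, in 0.7%.
- **That the plan's error rate is only 0.4% to 2%.** That is Fisher used alone, at common rates from 5% to 12%. The usual two-step rule gives 2.6% at a 10% rate and 4.6% at 15%.
- **That 5 to 19 points are gained in most sparse settings.** 52% of pairs is a bare majority. The larger gains need the rate to fall by two thirds or more, and the largest needs a zero rate in one arm. For a halving, power stays below 25% with either test.
- **That the change is free.** The added rejections raise the actual error rate in sparse data. Nor is the whole rule exact: its 5.7% peak remains, and with Boschloo it stands at 5.08% near a 19% rate.

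The objection that grades are not covered is also right. Boschloo's test is for 2 × 2 tables, whereas the plan's sentence covers status and grades together.

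**Conclusion.** The point holds as a modest efficiency gain for the present/absent comparison. Replacing only the Fisher branch never loses a rejection, so power cannot fall. It changes the verdict in two sparse patterns and their mirror images. The gain is about 5 to 19 points for large effects at low rates, about 1 to 4 points for a halving, and close to nothing when complications are common.

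This rests on the expected-count reading of a switching rule that the plan leaves open, on a two-sided 5% level for a comparison where none is stated, on 40 analysed per arm, and on assumed rates. It is a desirable refinement and does not affect the design or the mobility analysis.

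**What to change.** In Section 16, Secondary Analyses, replace the open choice of test for complication status with a stated rule: the uncorrected chi-square test when all expected counts are at least 5; otherwise Boschloo's exact test, two-sided at 5%, in place of Fisher's. Limit this to present/absent status and put the comparison of grades in a sentence of its own.

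The cost is a short text change. It needs no more patients or data, and the test is in standard software. The downsides are a less familiar test name and the higher actual error rate in sparse data: 0.4% to 1.5% at a common 5% rate, and 2.6% to 3.9% at 10%. The worst case of the whole rule stays at 5.7%. A further benefit is that the choice of test is fixed before the data are seen.

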1 OBJECTIVES

- To investigate objectively using evidence based randomized controlled trial the impact of early mobility (first day after the surgery) after any inpatient oncologic procedures on early recovery of postoperative course.
- Try to find out the minimum level of postoperative mobility that needed for early postoperative course recovery by objective assessment of range of movement for each participant using 3D motion tracking system (Xsens)

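### The stated aim of finding a minimum mobility level for early recovery has no analysis: nothing in the statistical plan relates recovery to the level of mobility reached

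*Combined protocol and SAP*

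**What the plan says.** **The aim.** The second of the two objectives in Section 1 is "Try to find out the minimum level of postoperative mobility that needed for early postoperative course recovery". Section 8 makes joint range of movement, measured with Xsens, the secondary endpoint, and states its purpose as "to identify the minimum required level of mobility for better early postoperative course recovery".

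**Recovery.** Section 8 describes the primary endpoint as "measuring early recovery of postoperative course by calculating early return of bowel motion (passing flatus and/or stool on which postoperative day" and then adds nausea or vomiting, chest symptoms, discharge, and 30-day complications and readmissions.

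**The analyses.** In Section 16, Primary Analysis: "The measures of mobility will each be modeled as a function of treatment group, time post-surgery, their two-way interaction", with random subject effects. Under Secondary Analyses: "The secondary objective is to evaluate the impact on post-surgical complications". Complication status and grade are compared between the arms with Fisher's exact or chi-square tests. The last sentence of that part reads "The association between complication status and changes in measures of mobility may be evaluated using logistic regression models". The sample size rests on "comparing the mean change (baseline to discharge) in a given mobility measure between groups".

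**The concern.** A question about the level of mobility needed for recovery requires recovery as the outcome and mobility level as the predictor. No model in Section 16 has that form. The minimum-level aim is not restated there either; the secondary objective named is a different one.

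A team that follows the plan to the letter would therefore have nothing to report on one of its two objectives. If it reported a minimum level anyway, the joint, the time window, the recovery outcome and the cut-point would all be chosen after seeing the data. With several joints and several recovery components available, that leaves wide room for a chance result to be presented as a mobility target.

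**Working it through.** **Step 1. The plan's own figure.** For 40 per arm, a difference of 0.63 SD and two-sided alpha 0.05, the normal approximation gives power = Φ(0.63 × √(40/2) − 1.96) = Φ(0.857) = 0.804. The exact t-test gives 0.795. The stated 80% reproduces, but it concerns a between-arm difference in mobility change and not the relation of recovery to mobility.

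**Step 2. Each analysis against the aim.**

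| Analysis in Section 16 | Outcome | Predictor | Relates recovery to mobility level? |
|---|---|---|---|
| Linear mixed model | Mobility | Arm, time, interaction | No: mobility is the response |
| Fisher's exact or chi-square | Complication status, grade | Arm | No: mobility does not enter |
| Logistic regression (optional) | Complication status | Change in mobility | No: change, and one component only |
| Power calculation | Change in mobility | Arm | No |

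The logistic sentence speaks of an association without naming the predictor. With a present/absent status in a logistic model, mobility change as predictor is the natural reading. No threshold, cut-point or dose-response method appears anywhere.

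**Step 3. What the optional model could detect.** The documents give no complication rate, so a range is assumed. For 80 patients and 80% power, detectable odds ratio per SD = exp[(1.96 + 0.84)/√(80·p·(1−p))]:

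- p = 10%: 2.84
- p = 20%: 2.19
- p = 30%: 1.98
- p = 40%: 1.90
- p = 50%: 1.87

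Only fairly strong associations would be seen, and an association with change would still not locate a level.

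**Step 4. What an analysis of level could deliver.** The inputs are assumptions: a hazard ratio of 1.3 per SD of early mobility, an arm difference in mobility of 0.63 SD, times recorded in days, and adjustment for arm and surgery type. The unadjusted 95% CI factor is exp(1.96/√events). The other columns come from a Cox simulation of 600 runs.

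| Events after the window | CI factor, unadjusted | CI factor, adjusted | Power | Curve CI factor, 1 SD below mean vs mean | Curve CI factor, 1.5 SD below |
|---|---|---|---|---|---|
| 80 | 1.25 | 1.28 | 0.57 | 1.36 | 1.74 |
| 60 | 1.29 | 1.34 | 0.43 | 1.44 | 1.93 |
| 40 | 1.36 | 1.44 | 0.32 | 1.59 | 2.33 |

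Check on the first row: SE = ln(1.28)/1.96 = 0.126, and Φ(ln(1.3)/0.126 − 1.96) = Φ(0.12) = 0.55, close to the simulated 0.57.

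The curve columns show why a single cut-point is out of reach. With a true hazard ratio of 1.3 per SD, the value at 1.5 SD below the mean is 1.3^(−1.5) = 0.67. Even with all 80 patients having events, the expected interval is 0.67/1.74 to 0.67 × 1.74, or about 0.39 to 1.17. At 1 SD below it is 0.77/1.36 to 0.77 × 1.36, or about 0.57 to 1.05. Both include no difference.

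**Step 5. Confounding.** Mobility level is not randomised. A simulation of a complication model on early mobility (3000 runs, no true effect) assumed an unmeasured factor correlated 0.3 to 0.5 with mobility and a log odds ratio of 0.5 to 1.0 for complications. False rejection at the 5% level was 7.1% to 31.1% unadjusted. It was 6.9% to 30.7% after adjustment for arm and a two-level surgery type whose underlying variable correlates 0.3 to 0.5 with that factor. Adjustment barely helps when surgery type captures the confounder only weakly.

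**The case against.** The best defence is that the aim is tentative. Section 1 speaks only of trying, and the minimum level is the purpose behind the secondary endpoint rather than the endpoint itself. Complications are a listed component of recovery, so the optional model does touch the question, and the mixed model does describe mobility levels over time. A trial of 80 patients could not deliver a threshold in any case.

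All of this is true. It supports an exploratory label and a more modest aim, but it does not supply an analysis: an exploratory objective still needs one, and describing mobility by arm and time says nothing about recovery at a given level.

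A reader might go further and infer two things that the documents do not support.

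- *That change carries little information about level.* The shared variance of change with discharge level is (1 − rk)²/(1 + k² − 2rk), where r is the baseline-discharge correlation and k the ratio of baseline to discharge SD. For r of 0.3 to 0.7 it is 75% to 77% at k = 0.5 but 0% to 13% at k = 1.5. The documents give neither r nor k, so no figure can be claimed. The point is only that change and level are different quantities.
- *That the optional model is biased because an in-hospital complication alters later mobility.* The sentence does not define its change period; baseline to discharge appears only in the power calculation. Neither direction nor size can be estimated.

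**Conclusion.** The gap stands on the text alone: one of the two objectives has no analysis, and the only neighbouring model is optional, uses change and covers complication status only. This should be corrected. It does not threaten the planned comparison of mobility between arms, and it would be wrong to read it as doing so.

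The gap itself rests on no numerical assumption. The power, curve and confounding figures do rest on assumed inputs. They show how much a repaired analysis could claim: a description of the level-response relation, with wide uncertainty, and no minimum level.

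**What to change.** **1. Reconcile the sections.** In Section 16, list the mobility-level question as an exploratory secondary objective beside the complications objective. Reword Sections 1 and 8 to describe the relation between early mobility level and recovery, in place of a promised minimum.

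**2. Replace the optional sentence with one pre-specified exploratory analysis.**

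- Predictor: one named Xsens range-of-movement summary in one fixed early window, for example postoperative day 1.
- Main outcomes: time from the end of that window to bowel function, and to discharge, among patients still at risk.
- Supporting outcomes: nausea or vomiting, chest symptoms, complications and readmissions arising after the window.
- Adjust for broad surgery type. Show results with and without arm, because adjusting for arm removes the randomised difference in mobility.
- Report a level-response curve with a confidence band, no cut-point and no confirmatory claim.

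**Cost.** Most of the data are already collected: Section 9 tracks both arms with Xsens, and records bowel function and symptoms, until discharge. The added work is wording in three sections and onset dates for symptoms and complications from the chart.

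**Downsides to state in the plan.** Events inside the window and later mobility data go unused. The two-day stay criterion in Section 3 should leave few discharges inside a day 1 window, but the number reaching bowel function by then is unknown. Precision is low and residual confounding may be substantial, so the results are hypothesis-generating.
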